4.3. Interim Analysis and Data Monitoring

No interim efficacy analyses or sample size re-estimations were planned to be conducted.

An external DSMB will be involved in the management of this study. The DSMB meeting will be held periodically for the duration of the study. The purpose of the DSMB is to review the progress of the study with special regard to safety and make recommendations to the Sponsor on how to handle any safety concerns that arise. Further details regarding the DSMB can be found in the DSMB charter which was finalized before the first meeting was scheduled.

Version 1.0 | 28-Feb-2025 Page 18 of 56

Statistical Analysis Plan, Sponsor: Cassava Sciences, Inc. Protocol Number: PTI-125-06 PCN Number: CASA215435

5. Analysis Populations

The following analysis sets were originally planned for this study:

- Intent-To-Treat (ITT) Analysis Set: The ITT analysis set includes all randomized participants.
- Intent-To-Treat mild (ITT-mild) Analysis Set: The ITT-mild analysis set includes all randomized participants who have a baseline MMSE of 21-27.
- Safety Analysis Set (SAF): The SAF analysis set includes all participants who received at least one dose of study treatment. All safety analyses will be completed in the SAF analysis set and participants will be included in the group based on the treatment received.
- **PK sub-study Analysis Set:** The PK sub-study analysis set includes all participants who sign the PK consent and/or re-consent form and have at least one non-missing post baseline PK assessment available.
- **Sub-study analysis sets:** Analysis sets for the Plasma, CSF, and imaging biomarkers will each be created as subsets of the ITT dataset that includes only those participants from the ITT analysis set who were in the relevant sub-studies.
- MRI sub-study Analysis Set: The MRI sub-study analysis set includes all participants who sign the MRI consent and/or re-consent form and have at least one non-missing post baseline MRI assessment available.

After the early termination, the following analysis sets were added:

- Modified intent-to-treat analysis set (mITT): The mITT analysis set is a subset of the ITT analysis set that includes all randomized participants with baseline P-tau181 ≥44 pg/ml or other evidence of amyloid pathology (e.g., Amyloid PET).

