6.1.3. Multiple Comparisons

The co-primary endpoints of ADAS-Cog12, and ADCS-ADL in the 100mg treatment arm will each be tested at p=0.05 using the mITT analysis set. Multiplicity among secondary endpoints for the 100 mg arm in the mITT analysis set will be controlled using a hierarchical, gatekeeping strategy. Secondary endpoints in the 100mg arm will be tested in the following order: iADRS, CDR-SB, ZBI, MMSE, and NPI-10. Testing will proceed in this order until the first non-significant p value (p > 0.05). The first endpoint with p > 0.05 and all subsequent endpoints in the order will be declared non-significant, and all endpoints preceding the first non-significant test will be declared significant. Endpoints that were significant in the 100mg arm will also be tested in the 50mg arm at P = 0.05.

For the set of significant endpoints in the 100 mg arm of the mITT analysis set, the corresponding endpoints in the mild subgroup (ITT-mild analysis set) will be tested. Testing for the mild cohort will proceed in the same order as for the secondary endpoints referenced above until the first non-significant p value. The first endpoint with p > 0.05 and all subsequent endpoints in the order will be declared non-significant, and all endpoints preceding the first non-significant test will be declared significant.

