8.1. Co-Primary Efficacy Analysis

Visit wise mean changes from baseline will be analyzed in the mITT analysis set using a restricted maximum likelihood (REML)-based repeated measures approach (MMRM). The MMRM analysis assumes a missing at random (MAR) missing-data mechanism, meaning that drop out is related to observed outcomes of the dependent variable and covariates, but not to the unobserved outcomes. The analysis will include the categorical, fixed effects of treatment group (3 levels), visit (7 levels), and pooled site, along with the continuous, fixed covariates of baseline value of the endpoint being analyzed (baseline), baseline MMSE score, and the interactions of treatment group, baseline, and baseline MMSE with visit. An unstructured (co)variance structure will be used to model the within-participant errors. If this analysis fails to converge, the following structures will be tested in this order, with the first structure yielding convergence to be used as the appropriate structure for that variable: heterogeneous Toeplitz, heterogeneous compound symmetric, and compound symmetric. If one of the structures other than unstructured is used, variance of the Maximum Likelihood Estimator (MLE) will be based on the Sandwich Estimator (empirical option in PROC MIXED statement). If none of the structures yield convergence, site will be removed from the model and the sequence of covariance structures will be refit as described above. The Kenward-Roger approximation will be used to estimate denominator degrees of freedom.

Significance tests for the between-treatment group differences will use a two-sided 0.05 level, with the co-primary analyses using the mITT analysis set.

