8.4. Subgroup Analyses of Efficacy Variables

The co-primary endpoints and iADRS will be analyzed in a subset of the mITT analysis set, termed the "amnestic subset", in which the following additional restrictions are applied: baseline CDR global score ≥ 1 and baseline score on the CDR memory domain ≥ 1 .

The co-primary endpoints and iADRS will be analyzed in the ITT analysis set by baseline severity, with subgroups defined as screening MMSE \geq 21 and \leq 27 versus MMSE < 21. An additional subgroup analysis for the co-primary endpoints and the iADRS will use screening MMSE \geq 20 and \leq 27 versus MMSE < 20. For these analyses, an MMRM model as previously described will be used, except that the model will have additional fixed effects for subgroup and its two-way interactions with treatment and Visit, and the 3-way subgroup-by-treatment-by-Visit interaction; and, baseline scores for the endpoint being analyzed and baseline MMSE and their interactions with Visit will be removed from the model due to their possible confounding with subgroup. Specifically, the analysis will include the categorical, fixed effects of treatment group, subgroup, pooled site, and Visit, along with the two-way interactions of treatment group with Visit and subgroup with Visit, and the three-way treatment group, subgroup, Visit interaction.

[figure not shown]
Similar models will be used to analyze subgroups by age (defined as < 65, 65-74 or ≥ 75), sex (defined as male or female), ethnicity (categories defined per FDA Guidance), race, ApoE4 genotype (defined as APOE4 non-carrier, carrier or homozygous) and medication use (cognitive enhancers, defined as yes or no).

There will be two additional subgroup analyses for the NPI-10. The first will include participants with a baseline NPI-10 score ≥ 2 . The second will analyze the agitation/aggression domain scores in participants with a non-zero baseline score in that domain.

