8.7. Time-Based Analyses

Mean changes from baseline in the co-primary endpoints will be described in terms of time savings. The mean change from baseline at Week 76 in the active arm will be mapped back to the time point at which the mean change in the placebo arm was equal to the active arm change at Week 76. A cubic spline interpolation will be used for precise time mapping between visits. Similar mappings will be done for the mean changes \pm the SE of the mean changes. If a time mapping is outside the range spanned by the reference trajectory (e.g., mapping standard errors near the beginning or end of follow-up), time will be mapped off the range spanned by the reference trajectory via the line connecting the first visit for change from baseline (0, 0) for change from baseline measures and last visit measures. This time component test will be done based on all participants and for the mild and moderate subgroups.

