T14.2.1.2.14	ITT	Summary of Change from Baseline to Week 76 in ADAS-Cog 12 Total Score by Visit and Treatment Stratified by Baseline Severity Group
T14.2.1.2.15	ITT	Summary of Change from Baseline to Week 76 in ADAS-Cog 12 Total Score by Visit and Treatment Stratified by Baseline Plasma P-Tau 181 Level
T14.2.1.2.16	ITT	Summary of Change from Baseline to Week 76 in ADAS-Cog 12 Total Score by Visit and Treatment: Responder Analysis
T14.2.1.2.17	ITT	Summary of Change from Baseline to Week 76 in ADAS-Cog 12 Total Score by Visit and Treatment Mild (21-27)/Moderate(<21) AD Status: Responder Analysis
T14.2.1.2.18	ITT	Summary of Change from Baseline to Week 76 in ADAS-Cog 12 Total Score by Visit and Treatment: Mild to Moderate Progression Analysis
T14.2.1.2.19	ITT	Summary of Change from Baseline to Week 76 in ADAS-Cog 12 Total Score by Visit and Treatment: Moderate to Severe Progression Analysis
T14.2.1.2.20	ITT	Summary of Change from Baseline to Week 76 in ADAS-Cog 12 Total Score by Visit and Treatment: Time Component Test
T14.2.1.6.1	Pooled	Summary of Change from Baseline to Week 52 in ADAS-Cog 12 Total Score by Visit and Treatment
T14.2.1.6.2	Pooled	Summary of Change from Baseline to Week 52 in ADAS-Cog 12 Total Score by Visit and Treatment Stratified by Baseline Severity Group
T14.2.1.6.3	Pooled	Summary of Change from Baseline to Week 52 in ADAS-Cog 12 Total Score by Visit and Treatment Stratified by Baseline Plasma P-Tau Level
T14.2.2.1.1	mITT	Summary of Change from Baseline to Week 76 in ADCS-ADL Total Score by Visit and Treatment
T14.2.2.2.1	ITT	Summary of Change from Baseline to Week 76 in ADCS-ADL Total Score by Visit and Treatment
T14.2.2.3.1	cITT	Summary of Change from Baseline to Week 76 in ADCS-ADL Total Score by Visit and Treatment
T14.2.2.4.1	ITT-mild	Summary of Change from Baseline to Week 76 in ADCS-ADL Total Score by Visit and Treatment

Version 1.0 | 28-Feb-2025 Page 42 of 56

T142212	ITT	Summary of Change from Baseline to Week 76 in ADCS-ADL Total
T14.2.2.1.2	mITT	Score by Visit and Treatment: Imputation Missing Not at Random
T14.2.2.1.3	mITT	Summary of Change from Baseline to Week 76 in ADCS-ADL Total Score by Visit and Treatment; Post Baseline Dose Change or Concomittant Medication Censoring Sensitivity Analysis
T14.2.2.1.4	mITT	Summary of Change from Baseline to Week 76 in ADCS-ADL Total Score by Visit and Treatment; Intercurrent Event Sensitivity analysis

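### The co-primary result is estimated in mITT, but the time-saved, responder, progression and main subgroup analyses are planned in ITT only, so none is run in the primary population

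*SAP*

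**What the plan says.** **Primary population.** SAP 3.2 changes the population of the primary estimand to participants with baseline P-tau181 of at least 44 pg/ml or other evidence of amyloid pathology. SAP 8.1 follows: "Visit wise mean changes from baseline will be analyzed in the mITT analysis set", and it closes "with the co-primary analyses using the mITT analysis set". In SAP 6.1.3 the two co-primary endpoints in the 100 mg arm "will each be tested at p=0.05 using the mITT analysis set", and the 100 mg secondary hierarchy uses the same set. SAP section 5 defines the sets: "The ITT analysis set includes all randomized participants", and "The mITT analysis set is a subset of the ITT analysis set".

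**Supportive analyses.** SAP 8.4 states: "The co-primary endpoints and iADRS will be analyzed in the ITT analysis set by baseline severity". It then applies similar models to age, sex, ethnicity, race, ApoE4 and medication use. SAP 8.5 (responders) and 8.6 (progression) refer to all participants. SAP 8.7 begins by saying that it will describe the co-primary mean changes as time savings, and ends: "This time component test will be done based on all participants and for the mild and moderate subgroups".

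**Output lists.** Table 6 settles what all participants means. The row for "Summary of Change from Baseline to Week 76 in ADAS-Cog 12 Total Score by Visit and Treatment: Time Component Test" (T14.2.1.2.20) carries the population label ITT. Table 9 repeats the label for the matching figure.

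**The concern.** A time saving is a restatement of a treatment difference against a placebo trajectory. If the co-primary difference comes from mITT and the weeks saved come from ITT means, then both the difference and the reference trajectory belong to another set, and the weeks do not translate the co-primary result. In the same way, the checks of consistency by age, sex or ApoE4 are made around the ITT estimate and not around the estimate on which the trial is judged.

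SAP 2.2 expects the effect to be larger in mITT, so the plan itself gives no ground for assuming that the two sets will agree. The pattern looks like an incomplete update. mITT was carried into the disposition percentages, a baseline table, the missing-not-at-random, medication and death sensitivity analyses and the amnestic subset, but not into these outputs, and no reason is given.

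**Working it through.** **Step 1: populations side by side** (SAP text against Tables 6 and 9).

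| Analysis | Text | ADAS-Cog12 rows | Label |
|---|---|---|---|
| Co-primary model | 8.1: mITT | T14.2.1.1.1 | mITT |
| Co-primary model, sensitivity | 8.1.1: ITT | T14.2.1.2.1 | ITT |
| Severity and demographic subgroups, ApoE4, medication | 8.4: ITT, then similar models | T14.2.1.2.6 to .13 | ITT |
| Responder | 8.5: all participants | T14.2.1.2.16, .17 | ITT |
| Progression | 8.6: all participants | T14.2.1.2.18, .19 | ITT |
| Time saved | 8.7: all participants | T14.2.1.2.20 | ITT |

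The ADCS-ADL rows (T14.2.2.2.6 to .13 and .16 to .20), the iADRS subgroup rows (T14.2.3.2.6 to .13) and the NPI-10 responder row (T14.2.5.7.1) are also ITT. So are the composite-severity and P-tau181 subgroups (.14 and .15). The only 8.4 subgroup analysis placed in mITT is the amnestic subset. The P-tau181 subgroup does not fill the gap: it is a median split, whereas mITT uses a cut at 44 pg/ml and also admits other amyloid evidence.

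**Step 2: the plan's own figures** (SAP 2.2). Placebo decline is 6.0 points, SD 10.0, and the difference 45%, so the planned effect is 0.45 × 6.0 = 2.7 points. With two-sided alpha 0.05 and 90% power this gives 289 per group, as stated (power 90.1%). Dropout: 289/0.8 = 361.25, against about 361 stated.

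**Step 3: illustration for time saved.** Let q be the share of ITT outside mITT. It is not in the documents; 10% to 40% is assumed. Assume a 2.7-point effect in mITT, none outside, and a linear placebo decline of 6.0 points over 76 weeks in both parts.

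- mITT: 76 × 2.7/6.0 = 34.2 weeks.
- ITT: 34.2 × (1 − q).

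| q | ITT difference (points) | ITT weeks saved |
|---|---|---|
| 0.1 | 2.43 | 30.8 |
| 0.2 | 2.16 | 27.4 |
| 0.3 | 1.89 | 23.9 |
| 0.4 | 1.62 | 20.5 |

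**Step 4: how much this depends on the assumptions.**

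- *Slower decline outside.* If those outside decline at a fraction r of the mITT rate, still with no benefit, the ITT figure is 34.2 × (1 − q)/[(1 − q) + qr]. At q = 0.4 and r = 0.5 this is 34.2 × 0.6/0.8 = 25.65 weeks, a 25% loss instead of 40%. At r = 0 the loss is nil.
- *Some effect outside.* Suppose the effect in ITT is the planned one and the effect in mITT is just large enough to keep power, a ratio of 1/√(1 − q). The ITT effect is then smaller than the mITT effect by 1 − √(1 − q): about 5% at q = 0.1 and 23% at q = 0.4. The implied effect outside, relative to that in mITT, is [√(1 − q) − (1 − q)]/q, or 49% and 44%.
- *Equal effect and equal decline.* The two sets give the same figure.

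**The case against.** The labels in Table 6 are not in dispute. The case on the other side concerns what follows from them.

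- **ITT is related to the primary set.** mITT is nested in ITT, so every mITT participant is in these analyses, and the co-primary model is also run in ITT (SAP 8.1.1). Each ITT result therefore has a matching ITT co-primary estimate. This stands: a reader might infer that these analyses say nothing about the primary result, and the documents do not support that. They support only that none is run in the primary population.
- **The mITT time saving is nearly available.** The visit-wise mITT means are already planned (T14.2.1.1.1, T14.2.2.1.1), and SAP section 1 allows post-hoc work. True, but that section also requires unplanned analyses to be identified as such, so an mITT time saving produced later would carry a post-hoc label.
- **The size is not anchored.** A reader might infer from SAP 2.2 that the effect outside mITT is near zero, and so that the ITT figures must be 10% to 40% too small. SAP 2.2 says only that a larger effect should make up for the smaller sample. Nothing in the documents fixes q, and all participants needed biomarker evidence at entry (protocol 5.2, criterion 5). This stands.
- **ITT is the protocol's set.** Protocol 11.2 places all efficacy analyses in ITT, and mITT was added after termination. SAP 8.4 also distinguishes its ITT mild/moderate comparison from the ITT-mild analyses of 8.2 and gives each its own purpose. This stands against replacing or demoting ITT, but not against adding mITT.
- **No decision depends on these analyses.** They are outside the hierarchy in SAP 6.1.3. True, and this limits the weight of the point.

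**Conclusion.** The mismatch is real and can be read directly from the SAP text and its output lists. It matters most for 8.7, which says that it re-expresses the co-primary mean changes but takes them from ITT.

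Its size cannot be stated. It depends on three things that the documents do not give: the share outside mITT, the effect there and the placebo decline there. The 30.8 to 20.5 weeks against 34.2 is a conditional illustration that rests on no effect outside mITT and equal linear decline in both parts. It is not a prediction, and SAP 2.2 does not imply it. Under milder assumptions the gap shrinks, and it can vanish. Neither the type I error nor the co-primary tests are affected. This is a minor, supportive improvement.

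**What to change.** Before unblinding, amend the SAP as follows:

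- In 8.7, add an mITT version, and state that the time saving quoted beside the co-primary result is the mITT one.
- In 8.4 (severity, age, sex, race, ethnicity, ApoE4, medication), 8.5 and 8.6, add mITT versions.
- Add the matching mITT rows to Tables 6 and 9.
- Keep all ITT versions, including the mild/moderate comparison in 8.4 that is set alongside the ITT-mild analyses.
- In 8.5, 8.6 and 8.7, name the analysis sets in place of the reference to all participants.

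The cost is wording, extra table and figure rows, and a second run of existing programs. The drawback is smaller subgroup cells in mITT, on top of the data lost to early termination. The retained ITT versions partly cover that.

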8.8. Pooling With Other Studies

Data from Protocol PTI-125-06 will be pooled with data from Protocol PTI-125-07. These pooled analyses will include data from weeks 0-52 from Protocol PTI-125-06 to match the duration of Protocol PTI-125-07. Objectives and estimands for the pooled data will mirror those in Protocol

Version 1.0 | 28-Feb-2025 Page 30 of 56

PTI-125-07. Analyses will also be similar but will include an additional categorical fixed effect of study. These pooled data will be analyzed using the co-primary and multiplicity adjusted secondary endpoints and by the subgroups defined by baseline composite severity / baseline P-tau categories.

Additional analyses may be applied to the pooled data based on the findings of the PTI-125-06 study.

9. Safety and Tolerability Analysis

All safety analyses will be performed on the safety analysis set.

Safety measures including AEs, clinical laboratory values, physical examination findings, neurologic examination findings, vital signs, ECGs, and concomitant medication usage will be summarized descriptively. No inferential statistical tests will be performed, unless otherwise specified. For quantitative variables, descriptive statistics including number of observations, mean, median, standard deviation, minimum, and maximum will be presented for observed and change from baseline values at each study visit. Qualitative variables will be summarized using counts and percentages.

For all safety and tolerability analyses, participants will be analyzed by the actual treatment and dose received and, if applicable, overall.

All safety and tolerability data will be presented in participant listings.

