# 7.1.6. Weeks 28 and 52 Follow-up Visits

Subjects will return to clinic for these scheduled visits within  $a \pm 5$ -day "window." On the Week 28 Visit, subjects in the tau PET sub-study should come to the clinic before taking their a.m. dose and have their PK blood sample collected prior to their dose.

- Vital signs (blood pressure [supine], temperature and pulse)
- Weight
- Brief physical and neurologic examination
- Adverse event monitoring
- Use of concomitant medications
- eCOA order of administration
  - Note: it is acceptable to simultaneously administer the study partner assessments in parallel with subject assessments (separate, qualified raters in separate rooms). When administered in parallel, the eCOA order of administration should be maintained (ADAS-cog12, MMSE and then C-SSRS for the subject; ADCS-ADL, NPI and then ZBI for the study partner).
    - ADAS-Cog12 (whenever possible, within 1 h of the time of day administered at the Baseline Visit (Study Day 1), and by the same rater)
    - ADCS-ADL
    - MMSE
    - NPI
    - ZBI
    - C-SSRS Since Last Visit version
- Clinical laboratory tests (blood and urine)
- For those 270 subjects participating in the amyloid or tau PET and Plasma Biomarker sub-studies, collect their Week 28 and Week 52 blood samples (including PK at Week 28 for those in the tau PET sub-study)

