8.2. Secondary Efficacy Analysis

[figure not shown]
The following secondary endpoints will be analyzed in the mITT, ITT, cITT, and ITT-mild analysis sets: iADRS, MMSE, NPI-10, and ZBI. The MMRM model as described for the primary analyses will be used, with the exception for MMSE where the baseline value for the endpoint being analyzed is the MMSE baseline; therefore, the model for MMSE will include the categorical fixed effects of treatment group, Visit, and pooled site, along with the continuous, fixed covariate of baseline MMSE score and the interactions of treatment group and baseline MMSE with Visit.

The CDR-SB is collected only at Screening and Week 76 or ET/ED. Therefore, the CDR-SB will be analyzed using ANCOVA with a model that includes treatment group, pooled site, and baseline MMSE.

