T14.2.6.4.1	ITT-mild	Summary of Change from Baseline to Week 76 in ZBI Total Score by Visit and Treatment
T14.2.6.6.1	Pooled	Summary of Change from Baseline to Week 52 in ZBI Total Score by Visit and Treatment
T14.2.6.6.2	Pooled	Summary of Change from Baseline to Week 52 in ZBI Total Score by Visit and Treatment Stratified by Baseline Severity Group
T14.2.6.6.3	Pooled	Summary of Change from Baseline to Week 52 in ZBI Total Score by Visit and Treatment Stratified by Baseline Plasma P-Tau Level
T14.2.7.1.1	mITT	Summary of Change from Baseline to Week 76 in CDR-SB Total Score by Visit and Treatment
T14.2.7.2.1	ITT	Summary of Change from Baseline to Week 76 in CDR-SB Total Score by Visit and Treatment
T14.2.7.3.1	cITT	Summary of Change from Baseline to Week 76 in CDR-SB Total Score by Visit and Treatment
T14.2.7.4.1	ITT-mild	Summary of Change from Baseline to Week 76 in CDR-SB Total Score by Visit and Treatment
T14.2.7.6.1	Pooled	Summary of Change from Baseline to Week 52 in CDR-SB Total Score by Visit and Treatment
T14.2.7.6.2	Pooled	Summary of Change from Baseline to Week 52 in CDR-SB Total Score by Visit and Treatment Stratified by Baseline Severity Group
T14.2.7.6.3	Pooled	Summary of Change from Baseline to Week 52 in CDR-SB Total Score by Visit and Treatment Stratified by Baseline Plasma P-Tau Level
T14.2.8.1.1	ITT-plasma	Summary of Change from Baseline to week 76 in Plasma P-Tau 217 by Visit and Treatment
T14.2.8.1.2	ITT-CSF	Summary of Change from Baseline to week 76 in CSF P-Tau 217 by Visit and Treatment
	•	

Version 1.0 | 28-Feb-2025 Page 45 of 56

T14.2.9.1.1	ITT-plasma	Summary of Change from Baseline to week 76 in Plasma Total Tau by Visit and Treatment
T14.2.9.1.2	ITT-CSF	Summary of Change from Baseline to week 76 in CSF Total Tau by Visit and Treatment
T14.2.10.1.1	ITT-plasma	Summary of Change from Baseline to week 76 in Plasma GFAP by Visit and Treatment
T14.2.10.1.2	ITT-CSF	Summary of Change from Baseline to week 76 in CSF GFAP by Visit and Treatment
T14.2.11.1.1	ITT-plasma	Summary of Change from Baseline to week 76 in Plasma NfL by Visit and Treatment
T14.2.11.1.2	ITT-CSF	Summary of Change from Baseline to week 76 in CSF NfL by Visit and Treatment
T14.2.12.1.1	PET	Summary of Change from Baseline to week 76 in tau PET by Visit and Treatment
T14.2.12.1.2	PET	Summary of Change from Baseline to week 76 in amyloid PET by Visit and Treatment
T14.2.13.1.1	MRI	Summary of Change from Baseline to week 76 in Whole Brain Volume by Visit and Treatment

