F14.2.5.6.1	ITT	Summary of Change from Baseline to Week 76 in NPI-10 Agitation and Aggression Domain Scores by Visit and Treatment in Participants with a Non-Zero Baseline Score for that Domain
F14.2.5.7.1	ITT	Summary of Change from Baseline to Week 76 in NPI-10 Total Score by Visit and Treatment: Responder Analysis
F14.2.5.6.1	Pooled	Summary of Change from Baseline to Week 52 in NPI-10 Total Score by Visit and Treatment
F14.2.5.6.2	Pooled	Summary of Change from Baseline to Week 52 in NPI-10 Total Score by Visit and Treatment Stratified by Baseline Severity Group
F14.2.5.6.3	Pooled	Summary of Change from Baseline to Week 52 in NPI-10 Total Score by Visit and Treatment Stratified by Baseline Plasma P-Tau Level
F14.2.6.1.1	mITT	Summary of Change from Baseline to Week 76 in ZBI Total Score by Visit and Treatment
F14.2.6.2.1	ITT	Summary of Change from Baseline to Week 76 in ZBI Total Score by Visit and Treatment
F14.2.6.3.1	cITT	Summary of Change from Baseline to Week 76 in ZBI Total Score by Visit and Treatment
F14.2.6.4.1	ITT-mild	Summary of Change from Baseline to Week 76 in ZBI Total Score by Visit and Treatment
F14.2.6.6.1	Pooled	Summary of Change from Baseline to Week 52 in ZBI Total Score by Visit and Treatment
F14.2.6.6.2	Pooled	Summary of Change from Baseline to Week 52 in ZBI Total Score by Visit and Treatment Stratified by Baseline Severity Group
F14.2.6.6.3	Pooled	Summary of Change from Baseline to Week 52 in ZBI Total Score by Visit and Treatment Stratified by Baseline Plasma P-Tau Level
F14.2.7.1.1	mITT	Summary of Change from Baseline to Week 76 in CDR-SB Total Score by Visit and Treatment
F14.2.7.2.1	ITT	Summary of Change from Baseline to Week 76 in CDR-SB Total Score by Visit and Treatment
F14.2.7.3.1	cITT	Summary of Change from Baseline to Week 76 in CDR-SB Total Score by Visit and Treatment
F14.2.7.4.1	ITT-mild	Summary of Change from Baseline to Week 76 in CDR-SB Total Score by Visit and Treatment
F14.2.7.6.1	Pooled	Summary of Change from Baseline to Week 52 in CDR-SB Total Score by Visit and Treatment
F14.2.7.6.2	Pooled	Summary of Change from Baseline to Week 52 in CDR-SB Total Score by Visit and Treatment Stratified by Baseline Severity Group
F14.2.7.6.3	Pooled	Summary of Change from Baseline to Week 52 in CDR-SB Total Score by Visit and Treatment Stratified by Baseline Plasma P-Tau Level

Version 1.0 | 28-Feb-2025 Page 55 of 56

[figure not shown]

Figure Number	Population	Figure Title/Summary

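### Pooled Week 52 CDR-SB outputs are planned, but PTI-125-06 schedules no CDR at Week 52, so this trial supplies either nothing or only some early-termination values

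*SAP*

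**What the plan says.** SAP section 8.8 sets the data range: "These pooled analyses will include data from weeks 0-52 from Protocol PTI-125-06 to match the duration of Protocol PTI-125-07". It sets the endpoints: "These pooled data will be analyzed using the co-primary and multiplicity adjusted secondary endpoints". On the model it says: "Analyses will also be similar but will include an additional categorical fixed effect of study".

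CDR-SB belongs to that set. SAP section 6.1.3 states: "Secondary endpoints in the 100mg arm will be tested in the following order: iADRS, CDR-SB, ZBI, MMSE, and NPI-10". Section 13.2 accordingly lists pooled tables T14.2.7.6.1 to T14.2.7.6.3, the first titled "Summary of Change from Baseline to Week 52 in CDR-SB Total Score by Visit and Treatment". Section 13.5 lists three matching figures, one of them titled "Summary of Change from Baseline to Week 52 in CDR-SB Total Score by Visit and Treatment Stratified by Baseline Severity Group".

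The collection schedule is different. SAP section 8.2 says: "The CDR-SB is collected only at Screening and Week 76 or ET/ED". It therefore analyses CDR-SB by ANCOVA at a single time point. Protocol section 7.1.6 gives the battery for Weeks 28 and 52 as "ADAS-cog12, MMSE and then C-SSRS for the subject; ADCS-ADL, NPI and then ZBI for the study partner", with no CDR. Protocol Appendix A marks CDR only at Screening and Week 76 ET/ED, and protocol versions 1.0 and 2.0 have the same CDR schedule. Protocol sections 7.1.7 and 9 also ask for a CDR at early termination (ET), unless one was done in the preceding 30 days.

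**The concern.** Limiting this trial to Weeks 0-52 removes every Week 76 CDR-SB value, and no Week 52 value is scheduled to replace it. Because CDR-SB is analysed by ANCOVA and not by a repeated-measures model, the analysis cannot borrow from other visits.

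That leaves ET values, and the SAP does not say which of them count as Week 52. Section 4.2 sends ET data for both safety and efficacy to the windows in section 6.1.5. In 6.1.5, the rule that discards an ET value falling in a window where the assessment is not scheduled stands in the safety text. The efficacy text has no window table and no ET rule.

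If no ET value enters, the study effect required by 8.8 cannot be estimated and the pooled result rests on the sister study alone. If some enter, this trial is represented only by people who ended by about Week 52. Those may be a mixture of ordinary dropouts and participants stopped after the November 2024 announcement, and everyone who continued past the window is left out. The SAP treats administrative stopping as missing completely at random (section 6.1.4), but that does not make ordinary dropouts representative of the randomised groups.

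**Working it through.** **The plan's own figure.** The only stated size is for ADAS-Cog (SAP 2.2). With a difference of 0.45 × 6.0 = 2.7, SD 10, two-sided alpha 0.05 and 90% power:

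- n per group = 2 × (1.960 + 1.282)² × 10² / 2.7² = 288.3, so 289, as stated.
- 289 / 0.80 = 361.25. The plan uses 361 (strict rounding up gives 362), and 3 × 361 = 1,083.

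The plan gives no figure for the pooled CDR-SB analysis, so 1,083 serves only as the denominator below.

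**Scheduled post-baseline assessments within Weeks 0-52** (protocol Appendix A):

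| Endpoint | Visits | Week 52? |
|---|---|---|
| ADAS-Cog12, ADCS-ADL (hence iADRS), ZBI | Weeks 4, 16, 28, 40, 52 | Yes |
| MMSE, NPI | Weeks 28, 52 | Yes |
| CDR-SB | None | No |

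Scheduled Week 52 CDR-SB values from PTI-125-06: 0 of about 1,083.

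**What ET visits could add, by reading of the SAP:**

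- (a) The discard rule in 6.1.5 applies to efficacy. CDR is not scheduled at Week 52, so the values are dropped: 0.
- (b) ET values go to the nearest visit with a scheduled CDR. That visit is Week 76, which the 0-52 limit removes: 0.
- (c) ET values go to the nearest clinic visit. Only those in the Week 52 window remain.
- (d) Every ET value up to the end of that window is taken.

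**Counts for (c) and (d).** Assumptions: the planned 20% drop-out, exits spread evenly over Day 1-533, a CDR at every ET visit, and the Week 52 safety window of SAP Table 2.1 (Day 324-407, 84 days) borrowed for efficacy.

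- Dropouts: 0.20 × 1,083 = 216.6.
- (c): 216.6 × 84/533 = 34 (3.2%).
- (d): 216.6 × 407/533 = 165 (15.3%).

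**Varying exit timing.** Keep 20% overall, so the total cumulative hazard is −ln(0.80) = 0.2231, and split follow-up at Day 266.5 with a constant hazard in each half.

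- First-half hazard half that of the second: cumulative hazard 0.1059 at Day 323 and 0.1528 at Day 407. (c) = 1,083 × (e^−0.1059 − e^−0.1528) = 45; (d) = 1,083 × (1 − e^−0.1528) = 153.
- First-half hazard double that of the second: cumulative hazard 0.1645 and 0.1880. (c) = 21; (d) = 186.

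**Varying the drop-out rate** (even exits): 10% gives 17 for (c) and 83 for (d); 30% gives 51 and 248.

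**Stratified outputs.** Under (c), 34 values across three arms and the three severity tertiles of SAP 8.4 would be 34/9, or about 4 per cell if evenly spread.

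**The case against.** The strongest reply is that this is a carry-over in the output list. The same three pooled Week 52 titles are repeated for every clinical endpoint, section 6.1.3 gives the pooled analysis no alpha, and the trial's main results do not depend on it. The last two points stand and keep the matter from being a major one. The carry-over explanation is not enough, though, because the text of 8.8 itself brings CDR-SB in through the multiplicity-adjusted secondaries.

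A second reply is that (a) and (b) are the better supported readings. Both give zero, so the table would simply repeat the sister study's result under a misleading title, without selection bias. That is fair, and nothing in the SAP positively supports (d). But the SAP does not rule out (c) or (d), and the zero readings still leave a study effect that cannot be estimated.

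A third reply is that the counts are soft. This also stands. A literal cut at Day 365 would give 216.6 × 42/533 = 17 for (c) and 216.6 × 365/533 = 148 for (d). The drop-out rate moves the counts further, and section 6.1.4 expects more missing data than planned. The counts illustrate scale only; the zero scheduled values do not depend on them.

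Finally, 8.8 says the pooled objectives and estimands follow the PTI-125-07 protocol, which is not available here, so the pooled model could differ from this trial's ANCOVA. No model can recover Week 52 CDR-SB for people who continued, however, because 8.8 excludes their only post-baseline CDR.

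**Conclusion.** The concern holds. Followed as written, section 8.8 asks for a Week 52 CDR-SB change that this trial does not measure on schedule: 0 of about 1,083 participants. Six outputs are affected (three tables, three figures).

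Depending on an unwritten choice about ET values, this trial contributes 0, 0, about 34 (21 to 45 as exit timing varies) or about 165 (153 to 186). The last two rest on the assumptions listed above and leave out administrative stops, whose number the documents do not give. That the sister study supplies Week 52 CDR-SB values is itself an assumption from its 52-week duration.

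The consequence is a mislabelled or selected supportive result. The co-primary analyses, this trial's Week 76 CDR-SB analysis and the other pooled endpoints are not affected. It should be corrected, but it does not threaten the trial's main conclusions.

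**What to change.** In SAP section 8.8, list the pooled endpoints by name (ADAS-Cog12, ADCS-ADL, iADRS, ZBI, MMSE, NPI-10) and state that CDR-SB is not pooled because PTI-125-06 has no scheduled assessment within Weeks 0-52. Delete T14.2.7.6.1 to T14.2.7.6.3 and F14.2.7.6.1 to F14.2.7.6.3. If a joint view is wanted, present each study's own end-of-treatment CDR-SB result side by side, without pooling.

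The cost is one added sentence and six deleted outputs, with no new data. The pooled report loses one supportive endpoint. If the sponsor prefers to keep the outputs, 8.8 must say before unblinding which PTI-125-06 values enter and under which window. That closes the ambiguity, but the contribution would still be nil or confined to people who ended early.
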